6.1.2 Clinical Procedures/Assessments

6.1.2.1 Adverse Event (AE) Monitoring

The investigator or qualified designee will assess each patient to evaluate for potential new or worsening AEs as specified in the Trial Schedule Section 5.0 (during the trial treatment period, for 30 days following end of treatment and again at 90 days for serious adverse events and more frequently if clinically indicated). Adverse experiences will be graded and recorded throughout the trial and during the follow-up period according to NCI CTCAE Version 4.0. Toxicities will be characterized in terms regarding seriousness, causality, toxicity grading, and action taken with regard to trial treatment.

Please refer to section 6.2 for detailed information regarding the assessment and recording of AEs.

6.1.2.2 Full Physical Exam

The investigator or qualified designee will perform a complete physical exam during the screening period. Clinically significant abnormal findings should be recorded as medical history.

6.1.2.3 Directed Physical Exam

For cycles that do not require a full physical exam per the Trial Flow Chart, the investigator or qualified designee will perform a directed physical exam as clinically indicated prior to trial treatment administration on days 1, 8, and 15 of each cycle, and at treatment discontinuation.

6.1.2.4 Vital Signs

The investigator or qualified designee will take vital signs at screening, prior to the administration of each dose of trial treatment and at treatment discontinuation as specified in the Trial Schedule (Section 5.0). Vital signs should include temperature, pulse, respiratory rate, weight and blood pressure. Height will be measured at screening only.

6.1.2.5 Eastern Cooperative Oncology Group (ECOG) Performance Scale

The investigator or qualified designee will assess ECOG status (Appendix 4) at screening, prior to the administration of trial treatment, on days 1, 8, and 15 of each cycle, and at discontinuation of trial treatment as specified in the Trial Schedule.

6.1.2.6 Tumor Imaging and Assessment of Disease

The patient's pancreatic cancer will be evaluated by the investigator based on tumor assessments using RECIST 1.1 and iRECIST criteria (Appendix 5).

Tumor assessments for evaluation of response will be conducted using CT or MRI, approximately every 9 ± 1 weeks until trial discontinuation or disease progression, whichever is later. All sites of disease must be followed using the same baseline assessment method.

CT is the preferred imaging modality for this study. I.V. contrast should be administered, unless medically contraindicated.

If CT with I.V. contrast is contraindicated, the alternative is to acquire a CT of the chest without contrast and MRI of the abdomen and pelvis with gadolinium contrast.

Other protocols, such as non-contrast CT of chest abdomen pelvis, should not be performed. For CT scans oral contrast should be administered in addition to IV contrast. Radiolucent agents (e.g., water) are generally preferred over radiopaque agents (e.g., iodine and barium-based agents).

All target lesions will be measured by consistent imaging techniques for each patient throughout the trial. Suitable imaging techniques include CT-scan, or MRI. The same technique should be used for each evaluation in an individual patient. Copies of the scans must be available for review.

In addition, a central radiologist, blinded to the treatment assignment, will perform an independent read of each scan, assessing tumor response using RECIST 1.1 and iRECIST criteria (Appendix 5).

In the event that PD by RECIST 1.1 or iUPD is determined, a repeat scan must be performed within 4 - 6 weeks to confirm PD. Trial treatment may be continued during this time (past the initial PD assessment) but only if patient is clinically stable as defined by:

- No worsening of performance status

- No clinically relevant increase in disease related symptoms
- No requirement for intensified management of disease related symptoms (analgesics, radiation, palliative care)

If the investigator assesses a patient to have PD (defined by RECIST 1.1), the central radiologist will review the scan to confirm the PD, prior to the discontinuation of trial treatment.

CA19-9 assessments (or CEA or CA-125 for not expressers of CA19-9) will be taken at baseline and approximately every 21 days during the trial treatment period. All CA19-9 assessments must be assayed by the same laboratory for each patient. Disease progression will not be determined by CA19-9, however increases in CA19-9 may warrant the investigator to obtain radiographic assessments.

Note: In order to more precisely determine time to progression, the investigator is encouraged to obtain radiological assessments and CA19-9 values earlier if there is a strong clinical suspicion of disease progression. In order to either confirm or refute the clinical impression.

6.1.2.7 Blood Collection

Each patient will have two - 10 mL vials of blood collected at the following timepoints: baseline, 9 ± 1 weeks on trial treatment, at time of confirmed response (if applicable) and at the EOT. Blood samples will be processed for serum and for peripheral blood mononuclear cells (PBMCs). Viable PBMCs will be stored in Bamberker™ freezing media for later analysis of circulating immune cells by existing technologies, such as flow cytometry, CyTOF, single-cell RNA-Seq, and single cell ATAC-Seq, as well as various new technologies as they become available. Serum will be snap frozen and used to evaluate the impact of therapies on circulating cytokine levels (e.g. IL6) by ELISA and multiplex cytokine assays.

Blood samples will be sent and centrally analyzed by [REDACTED] and the [REDACTED].

Specific details for blood sample collection and handling will be provided to the investigative sites in the Trial Laboratory Manual.

6.1.2.8 Tumor Tissue Collection

All patients will be required to provide an archival tissue specimen. Archival tissue will be analyzed in a similar manner as described below for formalin fixed paraffin embedded (FFPE) biopsy samples. Specific details for archival tissue processing and distribution will be provided to the investigative sites in the Trial Laboratory Manual. Sites will be asked to indicate whether blocks will be available for additional sectioning at a later point in time if additional tissue is needed.

Patients will be provided with the following two additional options to provide fresh tumor tissue for the analysis as described below.

Patients will be provided the option to consent to provide fresh tissue samples from a newly obtained core or excisional biopsy of a tumor lesion if performed recently (within 30 days prior to Cycle 1/Day 1) and during their participation in the study should they be scheduled for a biopsy as part of their routine care during their participation in the study through the follow-up period.

Additionally, patients will also be provided with the option to consent to undergo a biopsy of a tumor lesion at baseline, at the completion of 3 cycles of treatment (9 weeks after starting trial treatment), or at the time of disease progression if prior to week 9, unless tumor is considered inaccessible or biopsy is otherwise considered not in the patients best interest. *Participation in this trial is therefore not contingent on the patient consenting to optional tumor biopsies for fresh tissue.*

For patients consenting to the optional tumor biopsy, a baseline tumor biopsy will be collected and used for profiling. If possible (patient condition permitting) this will be repeated after 9 ± 1 weeks on trial treatment, or at the time of disease progression. Each tumor biopsy will consist of approximately 5 passes, refer to Trial Laboratory Manual for more details. The site is asked to provide an image (CT image) of needle orientation. Alternatively, if the biopsy is performed under ultrasound guidance, the site is asked to provide details on which lesion and where that lesion is located on a diagnostic CT or MRI (i.e. CT series and slice number). This de-identified image will be sent to [REDACTED] [REDACTED] (refer to protocol section 6.1.5).

Tissue samples will be sent and centrally analyzed by [REDACTED] and the [REDACTED].

Two passes will be split evenly and processed for formalin-fixed paraffin (FFP) and optimal cutting temperature (OCT) embedding and samples will be centrally analyzed using existing technologies, such as immunohistochemistry, immunofluorescence, and RNA-in situ hybridization, as well as various new technologies as they become available to evaluate the following:

- Stromal/extracellular matrix content (e.g. collagen and hyaluronic acid)
- Quantity and quality of vascularization (e.g. CD31)
- Expression of pembrolizumab related targets (e.g. PD-1 and PD-L1)
- Presence/ distribution, and activation of key immune cell populations (e.g. cytotoxic T Cells, TAMs, MDSCs, and Tregs)
- Presence, distribution, and activation of other stromal cell populations, including fibroblasts (e.g. α SMA)

One pass will be immediately snap frozen for the following central analysis

- Analysis of bulk tumor RNA for VDR expression and VDR targets (e.g. CYP24A1)
- Analysis of bulk tumor RNA for Expression of VDR regulated inflammatory gene (e.g. IL6, CXCL1, CSF2, CXCLR)

Two passes will be immediately frozen in Bambanker™ freezing media for the following central analysis:

- Genomic analysis of T-cell receptor clonality by sequencing (a measure of intratumoral T cell response)

Bulk and single-cell analysis of mutational profiles, transcriptional profiles, and epigenetic states within tumors, including analysis of sorted tumor cell nuclei.

In the event that biopsy tissue becomes limiting for certain analyses, snap frozen and Bambanker™ frozen tissue may be used interchangeably where technically feasible.

Specific details for tumor tissue collection and handling will be provided to the investigative sites in the Trial Laboratory Manual.

6.1.3 Laboratory Procedures/Assessments

Safety laboratory tests for hematology, chemistry, and urinalysis (as detailed in Table 9) will be performed by the local laboratory for each investigational site at screening, baseline and throughout the trial treatment period. Serum vitamin D levels will be performed at screening. HBsAg and HCV RNA (qualitative) will be performed at screening if not performed within the last 3 months. Thyroid and Parathyroid function (T3, FT4 TSH, and PTH) will be performed as part of screening and every other cycle during the trial treatment period.

Table 9. Laboratory Tests – performed locally

| Hematology | Chemistry | Urinalysis | Other |
|------------------------------|----------------------------------|---|--|
| Hematocrit | Albumin | Blood | Serum β -human chorionic gonadotropin† |
| Hemoglobin | Alkaline phosphatase | Glucose | PT (INR) |
| Platelet count | Alanine aminotransferase (ALT) | Protein | aPTT |
| WBC (total and differential) | Aspartate aminotransferase (AST) | Specific gravity | Thyroid stimulating hormone (TSH) |
| Red Blood Cell Count | Lactate dehydrogenase (LDH) | Microscopic exam (If abnormal results are noted) | Total triiodothyronine (T3) |
| Absolute Neutrophil Count | Carbon Dioxide ‡ | | Free thyroxine (T4) |
| Absolute Lymphocyte Count | (CO ₂ or bicarbonate) | | PTH (parathyroid hormone) |
| | Uric Acid | | Serum vitamin D (25- |

| Hematology | Chemistry | Urinalysis | Other |
|--|--|------------|---------------------|
| | | | hydroxy vitamin D) |
| | Calcium | | HBsAG |
| | Chloride | | HCV RNA qualitative |
| | Glucose | | |
| | Phosphorus | | |
| | Potassium | | |
| | Sodium | | |
| | Magnesium | | |
| | Total Bilirubin | | |
| | Direct Bilirubin (If total bilirubin is elevated above the upper limit of normal) | | |
| | Total protein | | |
| | Blood Urea Nitrogen | | |
| | Creatinine | | |
| † Perform on women of childbearing potential (WOCBP) only. | | | |
| ‡ If considered standard of care in your region. | | | |

6.1.4 Patient Personalized Clinical Benefit (PPCB)

The exploratory objective to assess Patient Personalized Clinical Benefit (PPCB) will be evaluated based on the improvement in disease-related symptoms. The specific disease-related symptoms that are most bothersome for the individual patient will be identified at baseline and followed throughout the trial. Patients will use a trial-specific phone-based application to record the status of their three most bothersome disease-related symptoms at baseline, weekly during the treatment period, and at the EOT visit. The patient will be provided instructions and download and complete the app during the baseline C1/Day 1 visit. The patient will enter their responses directly into the APP via their mobile device using an assigned patient ID and therefore no protected health information (PHI) will be recorded. In the event that a patient does not have the type of mobile device required to access the APP, or the patient chooses not to complete the PPCB via the APP, the patient will be provided a paper questionnaire to complete. The site will record the reason the patient is not utilizing the APP in the source documents. Refer to Appendix 6 for more details on the PPCB App.

6.1.5 Quantitative Textural Analysis (QTA)

Quantitative Textural Analysis (QTA) will be used to explore differences in tumor and tissue texture between the two treatment arms of this trial using baseline, on treatment, and post treatment CT scans. Such information may provide a basis for establishing a complementary diagnostic biomarker that could 1) predict disease stability in the maintenance environment 2) provide an imaging signature that is associated with immune infiltrative activity, 3) allow a non-invasive method for detecting tumor and tissue texture changes related to vitamin D (paricalcitol) exposure and 4) identify other correlations of imaging to tumor biology, response to treatment, and laboratory assessments.

CT scans will be performed at each investigative site as per protocol schedule.

Sites will be provided instructions for sending de-identified CT scans [REDACTED] [REDACTED] for analysis. Images will be reviewed to ensure appropriate series, images and anatomic coverage is available and that all PHI has been removed. Only query-free studies will be forwarded for analysis. Query-free scans will be loaded onto [REDACTED] QTA analysis platform for textural analysis. Refer to Appendix 7 for specific information on the planned QTA analysis to be performed.

6.1.6 16S Gut Microbiome rRNA Analysis

The exploratory objective to monitor and compare the gut microbial communities will be evaluated using patient collected fecal samples. The differences in gut microbial communities within and between fecal samples will be compared using alpha and beta diversity metrics based on 16S rRNA sequencing. The DNA extraction and sequencing analysis will be performed at [REDACTED]. Refer to Appendix 8 for more specific information on the planned analysis to be performed. Specific details for sample handling and shipping will be provided to the investigative sites in the Trial Laboratory Manual.

Fecal samples are relatively easy to collect and non-invasive. They provide an indication of the gut microbiome which may be an indicator of general health, impact drug availability, and indicate the presence of communities associated with inflammation, digestive inefficiencies, and pathogens. Monitoring the gut microbiome may allow us to predict the risk of possible side effects of pembrolizumab (colitis and decreased appetite) and paricalcitol (decreased appetite).

Fecal samples will be collected by the patient at home during trial participation. Patients will be asked to collect two samples per treatment cycle. One fecal swab sample is to be collected within the 72 hours prior to Day 1 of each treatment cycle, and a second fecal swab sample within 24-72 hours after treatment on Day 1. The patient will also be asked to collect one final sample approximately 30 days following treatment discontinuation. Patients will be provided with collection instructions (refer to Appendix 9), collection container, sterile CultureSwabs in individual pre-labeled containers, and a biospecimen bag. Patients will collect fecal material in a collection container, and then transfer a pea size amount of fecal matter using the provided CultureSwabs, into the original pre-labeled fecal swab collection container, and place in the provided biospecimen bag. The patient will be asked to store the fecal samples in the freezer and deliver to the research site within 72 hours of collection (this will correspond with the patients' return to clinic - so it is not anticipated that additional clinic visits should be required).

6.1.6.1 *Withdrawal/Discontinuation*

When a patient discontinues/withdraws prior to trial completion, all applicable activities scheduled for the EOT visit should be performed at the time of discontinuation. Any adverse events which are present at the time of discontinuation/withdrawal should be followed in accordance with the safety requirements outlined in Section 6.2 - Assessing and Recording Adverse Events.

6.1.6.2 *Blinding/Unblinding*

This is a double-blind, randomized, placebo-controlled phase II trial with the identity of the treatment unknown to the patients, investigators and the Sponsor. Only the site pharmacist and unblinded trial monitor will be aware of the assigned treatment arm.

Investigators will be able to unblind in emergency situations when the identity of the treatment must be known in order to provide appropriate treatment. The sponsor must be contacted (if possible) prior to the treating investigator unblinding a patient.

Additionally, at the time of disease progression the treating investigator may request the unblinded treatment assignment for the patient. This will be provided by the unblinded trial monitor to the treating Investigator for the purposes of considering future treatment options. The remainder of the trial team will not have access to this unblinded treatment assignment.

Once a patient is unblinded he/she will not be allowed to continue on trial medication and will be considered an early withdrawal and will need to complete the required EOT procedures and necessary follow-up per section 6.1.5.3.

6.1.7 Visit Requirements

Visit requirements are outlined in Section 5.0 - Trial Schedule. Specific procedure-related details are provided above in Section 6.1 - Trial Procedures.

6.1.7.1 *Screening Period*

Screening of potential patients will be performed only after informed consent is obtained and within 21 days prior to first dose of trial medication (unless otherwise noted below). All necessary laboratory values and assessment reports must be available and reviewed prior to cycle 1/ day 1.

The following will be completed as part of the screening visit:

1. Written informed consent
2. Medical history including concurrent baseline conditions (using NCI CTCAE version 4.0; Appendix 3), prior cancer therapy (including documentation of prior surgery, adjuvant or neoadjuvant chemotherapy and radiotherapy)
3. Complete physical examination including height (cm) and weight (kg)
4. ECOG Performance Status (see Appendix 4)
5. Vital signs (blood pressure, pulse, respiratory rate, and temperature)
6. Computed tomography (CT) / magnetic resonance imaging (MRI) scan to document disease status (including chest, abdomen, pelvis, and other regions as clinically indicated. In addition, brain scan is required to exclude brain metastases if clinically

indicated only). If a CT scan was taken within 28 days prior to first dose, a new scan is not necessary. However, if a new scan is to be done, it should be performed within 10 ± 2 days prior to starting trial medication. Obtain De-identified Dicomm encoded CT scan for central lab (Appendix 7).

7. Electrocardiogram (ECG)
8. PT/INR and aPTT
9. Complete blood count (CBC) with differential and platelet count
10. Comprehensive serum chemistries (refer to Table 9)
11. TSH, T3, Free T4, and PTH
12. Serum vitamin D level
13. HBsAg and HCV RNA (qualitative) if not performed in the last 3 months
14. Urinalysis (refer to Table 9)
15. Serum β -HCG pregnancy test for women of child-bearing potential (refer to Section 4.7.2 for more details)
16. Concomitant medication notation (to include all medications taken within 30 days prior to enrollment)
17. For those patients consenting to the optional fresh tissue collection: Obtain fresh tissue from a newly obtained core or excisional biopsy if performed within the last 30 days prior to first dose of trial medication (C1/D1). Refer to Section 6.1.2.8.
18. For those patients consenting to the optional baseline biopsy: Fresh tissue is to be obtained up to 3 weeks (21 days) prior to first dose of trial medication (C1/D1). Refer to Section 6.1.2.8.
19. Obtain archival tumor specimen for all patients - as required for eligibility. Refer to Section 6.1.2.8.
20. Central Lab Blood Sample 2 X 10 mL vials . Refer to Section 6.1.2.7.
21. Provide Fecal Swab collection kit and review instructions with patient for return of sample on Cycle 1/Day 1. Refer to Section 6.1.6.
22. Investigator or qualified designee to review and record the patient's three most bothersome disease-related symptoms (as determined by the patient) to be followed during treatment period, via the Patient Personalized Clinical Benefit (PPCB) App – Refer to Appendix 6.

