4.1.2 Exclusion Criteria

Patients meeting the following criteria will NOT be eligible to participate in this trial:

1. Is currently participating and receiving trial therapy or has participated in a trial of an investigational agent and received trial therapy or used an investigational device within 4 weeks of the first dose of trial treatment.
2. Has a diagnosis of immunodeficiency or is receiving systemic steroid therapy or any other form of immunosuppressive therapy within 7 days prior to the first dose of trial treatment. The use of physiologic doses of corticosteroids may be approved after consultation with the Sponsor.
3. Has a known history of active TB (*Mycobacterium tuberculosis*).

4. Hypersensitivity to pembrolizumab or paricalcitol or any of its excipients.
5. Has had a prior anti-cancer monoclonal antibody (mAb) within 4 weeks prior to Cycle 1/ Day 1 or who has not recovered (i.e., \leq Grade 1 or at baseline) from adverse events due to agents administered more than 4 weeks earlier.
6. Has had prior chemotherapy, targeted small molecule therapy, or radiation therapy within 2 weeks prior to Cycle 1/ Day 1 or who has not recovered (i.e., \leq Grade 1 or at baseline) from adverse events due to a previously administered agent.

Note: Patients with \leq Grade 2 neuropathy are an exception to this criterion and may qualify for the trial.

Note: If patient received major surgery, they must have recovered adequately from the toxicity and/or complications from the intervention prior to starting therapy.

7. Has a known additional malignancy that is progressing or requires active treatment. Exceptions include basal cell carcinoma of the skin or squamous cell carcinoma of the skin that has undergone potentially curative therapy or in situ cervical cancer.
8. Has known active central nervous system (CNS) metastases and/or carcinomatous meningitis. Patients with previously treated brain metastases may participate provided they are stable (without evidence of progression by imaging for at least four weeks prior to the first dose of trial treatment and any neurologic symptoms have returned to baseline), have no evidence of new or enlarging brain metastases, and are not using steroids for at least 7 days prior to trial treatment. This exception does not include carcinomatous meningitis, which is excluded regardless of clinical stability.

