4.5.2 Prohibited Concomitant Medications

Patients are prohibited from receiving the following therapies during the Screening and Treatment Phase of this trial. For specific therapies there is a washout window prior to cycle 1/day 1, indicated below and per eligibility criteria in Section 4.1.

- Antineoplastic systemic chemotherapy or biological therapy. Prior anti-cancer monoclonal antibody (mAb) must be > 4 weeks prior to Cycle 1/Day 1.
- Immunotherapy
- Chemotherapy targeted small molecule therapy, or radiation therapy within 2 weeks prior to Cycle 1/Day 1.

Note: Radiation therapy to a symptomatic solitary lesion or to the brain may be allowed at the investigator's discretion.

- Investigational agents within 4 weeks prior to Cycle 1/Day 1
- Live vaccines within 30 days prior to the first dose of trial treatment and while participating in the trial. Examples of live vaccines include, but are not limited to, the following: measles, mumps, rubella, varicella/zoster, yellow fever, rabies, BCG, and typhoid vaccine.
- Systemic glucocorticoids in doses of ≥ 10 mg/day prednisone or equivalent for any purpose other than to modulate symptoms from an event of clinical interest of suspected immunologic etiology. The use of physiologic doses of corticosteroids may be approved after consultation with the Sponsor.
- Strong inhibitors of CYP3A, digitalis or its compounds, aluminum containing preparations should not be used during the trial due to their potential to interact with paricalcitol.
- Phosphate or vitamin-D related compounds should not be taken concomitantly with paricalcitol. Patients will be asked to report vitamin and nutritional supplement use at baseline and throughout the trial.

Patients who, in the assessment by the investigator, require the use of any of the aforementioned treatments for clinical management should be removed from the trial. Patients may receive other medications (not listed here as prohibited) that the investigator deems to be medically necessary.

The Exclusion Criteria describes other medications which are prohibited in this trial.

There are no prohibited therapies during the Post-Treatment Survival Follow-up Phase of the trial.

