5.0 Trial Schedule

The trial will consist of the following three periods:

Screening (SCN) Period: The screening period will take place only after informed consent is obtained and within the 21 days prior to C1/D1. The screening visit may be counted as the baseline visit if completed within 7 days of initial dosing on C1/D1.

Treatment Period: Patients will be treated at 21 ± 3 day intervals. Patient must begin cycle 1 within 21 days of signing the IRB approved informed consent document and after the screening assessments have been performed and reports have been reviewed to confirm eligibility. The patient will continue on maintenance therapy until there is evidence of clear-cut tumor progression, has treatment ending toxicities, or withdraws from treatment (refer to section 4.8). Table 7 below summarizes the Screen-Treatment Period Schedule.

Post Treatment Period: Patients will return to the investigative site for an End of Treatment (EOT) visit within 5 days after the last dose of trial treatment or before the initiation of a new anti-cancer treatment, whichever comes first (refer to Section 6.1.7.3). An additional mandatory Safety Follow-up visit should be conducted approximately 30 days after the last dose of trial treatment and before initiation of a new anti-cancer treatment, whichever comes first (6.1.7.4). WOCBP will be required to have a pregnancy test at this visit.

After the 30 day-FU visit, patients will then move into the Survival Phase and be contacted by telephone every 90 days thereafter until death, withdrawal of consent, or the end of the trial, whichever occurs first. The protocol approved contraceptive guidance (Section 4.7.2) must be followed for at least 120 days (for males) and 180 days (for WOCBP) after the last dose of trial treatment. Table 8 below summarizes the Post Treatment Period Schedule.

Footnotes for Table 7. Screen – Trial Treatment Period Schedule

- a. Written IRB-approved informed consent must be obtained prior to any screening assessments being performed.
- b. Documented medical history to include, demographics, concurrent baseline conditions (using NCI-CTCAE V4. Appendix 3), prior cancer treatment and surgeries.

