Day 3, 5, 8, 10, 12, 15, 17, and 19 (\pm 1 day) of each cycle

- Vital signs
- AEs using the NCI CTCAE (Appendix 3)
- Concomitant medication notation
- **Day 8 and 15 of each cycle only:** Directed physical exam, including weight
- **Day 8 and 15 of each cycle only:** ECOG Performance Status
- **Day 8 and 15 of each cycle only:** Hematology: CBC with differential and platelet count - results must be reviewed prior to paricalcitol administration
- **Day 8 and 15 of each cycle only:** Serum chemistries (refer to Table 9) - results must be reviewed prior to paricalcitol administration
- **Day 8 and 15 of each cycle only:** Patient to complete the Patient Personalized Clinical Benefit (PPCB) App (Appendix 6)
- **Day 19 Only:** Provide Fecal Swab collection kit and review instructions with patient for return of sample on Day 1 on next treatment cycle
- Paricalcitol administration

Week 9 (+/- 1 week)

- Optional repeat biopsy refer to Section 6.1.2.8
- Central Lab Blood Sample, 2 X 10 mL vials refer to Section 6.1.2.7

End of 3 treatment cycles (every 9 ± 1 weeks) until disease progression or end of trial, whichever comes first

- CT/MRI scan to evaluate disease status (using same imaging method as Baseline). Obtain De-identified dicomm encoded CT scan for central lab (Appendix 7).

Note: In order to more precisely determine time to progression, the investigator is encouraged to obtain radiological assessments and CA19-9 values earlier if there is a strong clinical suspicion of disease progression. In order to either confirm or refute the clinical impression.

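### The baseline central blood sample may be drawn up to 21 days before first dose with no minimum gap from last chemotherapy; a pre-dose draw at Cycle 1 Day 1 would be cleaner and costs almost nothing

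*Protocol*

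**What the plan says.** Protocol section 6.1.2.7 schedules the central blood samples at "baseline, 9 ± 1 weeks on trial treatment, at time of confirmed response (if applicable) and at the EOT". Serum is for circulating cytokines, to show the impact of therapy. Mononuclear cells are stored for later immune-cell analysis.

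In the visit lists, the pre-treatment draw appears once, as item 20 of the screening list in section 6.1.7.1: "Central Lab Blood Sample 2 X 10 mL vials". The item has no window of its own, so the general screening window of 21 days before first dose applies. The Day 1 list in section 6.1.7.2 has no central blood sample. The next one is at week 9 ± 1: "Central Lab Blood Sample, 2 X 10 mL vials refer to Section 6.1.2.7".

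Three other rules bear on the timing:

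- Section 5.0: "The screening visit may be counted as the baseline visit if completed within 7 days of initial dosing on C1/D1".
- Section 4.1.2, exclusion 6: "Has had prior chemotherapy, targeted small molecule therapy, or radiation therapy within 2 weeks prior to Cycle 1/ Day 1".
- Section 4.5.2: "Patients are prohibited from receiving the following therapies during the Screening and Treatment Phase of this trial". Its first bullet is systemic anticancer chemotherapy.

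The optional baseline biopsy has a similar window: "Fresh tissue is to be obtained up to 3 weeks (21 days) prior to first dose of trial medication". Fresh tissue from a routine-care biopsy may be up to 30 days old.

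**The concern.** Every eligible patient has had first-line chemotherapy for metastatic disease, so many may have had it recently. The washout protects the first dose of trial drug. It does not protect the baseline sample, which may come up to three weeks before that dose. A patient whose last chemotherapy was shortly before consent can have the baseline sample taken a few days later, while the week-9 sample is always well clear of chemotherapy.

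Any change from baseline to week 9 within an arm could then combine recovery from chemotherapy with the effect of the trial regimen. The interval since chemotherapy also differs between patients, which adds scatter to the change scores in at most 12 patients per arm.

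Separately, the sections do not agree on what baseline means for this sample. A draw on days -21 to -8 falls outside the 7-day rule in section 5.0, and the visit list gives no later draw to replace it.

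**Working it through.** The plan states no figure on this point, so there is none to reproduce. C1/D1 is counted as day 0.

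**1. Gaps that the rules allow.** The inputs are the draw window (day -21 to day 0), last chemotherapy no later than day -14, no chemotherapy during screening (so the draw follows the last dose), and week 9 ± 1 (days 56 to 70).

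| Draw day | Minimum days since chemotherapy | Days to week-9 sample |
|---|---|---|
| -21 | 0 | 77 to 91 |
| -14 | 0 | 70 to 84 |
| -7 | 7 | 63 to 77 |
| 0 (C1/D1) | 14 | 56 to 70 |

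The minimum gap is the larger of 0 and (draw day + 14). The interval to week 9 is 56 or 70 minus the draw day. The week-9 sample is at least 14 + 56 = 70 days after chemotherapy.

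An early draw is allowed but not required. With last chemotherapy on day -35, a draw on day -21 is already 14 days clear.

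**2. How often the gap would be under 14 days.** The documents do not give the distribution of last chemotherapy dates, so this is assumed. Take last chemotherapy on each day from a start day to day -15, and the draw on each later day from -21 to -1. Count the permitted pairs:

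| Start of chemotherapy range | Pairs under 14 days / all pairs | Share |
|---|---|---|
| Day -28 | 161 / 266 | 61% |
| Day -35 | 182 / 413 | 44% |
| Day -42 | 182 / 560 | 33% |

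If each patient, rather than each pair, has equal weight, the shares are 63%, 46% and 35%. In the day -28 case, 24% of pairs are under 7 days.

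**3. Carry-over into baseline.** Assume that chemotherapy shifts a marker by 1 SD and that the shift decays as 0.5^(days since dose / h), with half-time h of 5 or 10 days. Averaged over the day -28 case:

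| Draw | Mean carry-over (SD) | Between-patient SD of carry-over |
|---|---|---|
| Screening, after last dose | 0.27 (h = 5) to 0.48 (h = 10) | 0.20 to 0.22 |
| C1/D1 | 0.06 to 0.23 | 0.03 to 0.06 |

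By week 9 the remainder is at most 0.5^(70/10) = 0.008 SD. Almost all of the baseline carry-over therefore passes into the within-arm change.

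**4. Effect on the comparison between arms.** Allocation is 1:1 with the same blood schedule in both arms, so the expected carry-over is equal and cancels from the difference. In a simulation with 12 per arm, a recovery shift of 0.5, 1.0 or 1.5 SD in a random half of patients moved the within-arm mean change by 0.25, 0.50 and 0.75 SD. It moved the between-arm difference by 0.00, and two-sided type I error stayed at about 5%.

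For the cost in precision, take a change-score SD of 1 (assumed), a true difference of 1.2 SD and a two-sided 5% t test on 22 degrees of freedom. The noncentrality is 1.2 / (SD × √(2/12)).

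- No carry-over: 1.2 / 0.408 = 2.94, power 80%.
- Carry-over SD 0.20: total SD √(1 + 0.20²) = 1.020, power 79%.
- Carry-over SD 0.22: total SD √(1 + 0.22²) = 1.024, noncentrality 2.87, power 78%.

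**The case against.** The strongest reply is that no specified analysis is harmed. Protocol section 8 and the SAP, which is confined to clinical endpoints, contain no analysis of the blood samples. The change analyses in section 8.3.5.3 use biopsies and compare arms, with a baseline-adjusted regression as a sensitivity analysis. This stands, and it limits the point to supportive work.

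A second reply is that section 6.1.2.7 says baseline, and section 5.0 accepts screening as baseline only within 7 days of dosing. If that rule governs the draw, the day -28 assumption gives 21 of 98 pairs (21%) under 14 days and none under 7. This would remove much of the problem. However, the visit list does not apply the rule to item 20, and it offers no Day 1 draw when screening was earlier. At the least, the sections need to agree.

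Third, the Table 7 grid is not legible in the text available to us, and the laboratory manual is a separate document. A C1/D1 draw marked in either cannot be ruled out. None of the legible Table 7 footnotes mentions one.

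Three stronger readings are tempting, and the documents do not support them:

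- **The sample could precede the final chemotherapy dose.** Exclusion 6 alone would allow this, but section 4.5.2 bars systemic chemotherapy during screening, and screening starts only after consent.
- **The early draw is the typical case.** Inclusion 3 sets no maximum interval since chemotherapy, so the share depends on dates that the documents do not give.
- **The between-arm result is biased.** Randomisation and the common schedule prevent this. Chance imbalance remains possible with 12 per arm.

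**Conclusion.** The point holds as a cheap improvement. As listed, the baseline central blood sample may be taken within 14 days of chemotherapy and outside the protocol's own 7-day baseline rule. Within-arm change to week 9 would then be hard to attribute to the trial regimen.

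The share of early samples runs from about 60% to a third as the assumed range of last chemotherapy dates widens from four to six weeks before dosing. The within-arm shift of 0.27 to 0.48 SD rests on an assumed 1 SD chemotherapy effect and a half-time of 5 to 10 days. The loss for a between-arm comparison is small, one to two percentage points of power. The larger losses in a harsher scenario (to 71% or 61%) need a carry-over SD of 0.5 or 0.75, more than twice the 0.20 to 0.22 found here.

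The primary endpoint, overall survival and toxicity are unaffected.

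**What to change.** Move the baseline central blood sample from screening item 20 in section 6.1.7.1 to the Cycle 1 Day 1 list in section 6.1.7.2, before the first paricalcitol or placebo dose. Then make sections 5.0, 6.1.2.7, 6.1.7.1 and 6.1.7.2 and the Table 7 grid agree on that timepoint. Every baseline sample will then be at least 14 days after chemotherapy and 56 to 70 days before the week-9 sample, instead of 56 to 91. Some carry-over may remain (0.06 to 0.23 SD under the assumptions above), but it will be smaller and more uniform.

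The cost is one line moved and the matching schedule entry. Patients already attend that day, and laboratory blood work is listed there, so no visit or blood volume is added. The small downside is that patients who fail screening contribute no sample.

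For the optional baseline biopsy and the routine-care fresh tissue, record days since last chemotherapy as a descriptor only. Do not exclude samples taken within 14 days. Under the day -28 assumption that would leave about 12 × (1 − 0.61) = 5 per arm even if every patient consented, and consent is optional.
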